3.2. Analysis methods

3.2.1. Efficacy

3.2.1.1. Primary efficacy analysis

The primary efficacy analysis will be performed after 61 BR events have been observed and this analysis will be repeated on the number of BR events observed until the end of study.

The primary efficacy analyses of BRFS will be performed on the ITT population (cf. Section 3.2.10 for derived BRFS).

An exploratory analysis will be performed on the mITT and PP population (only on the total number of BR at the end of the study).

BRFS will be provided by treatment group. A log-rank test (two-sided) will be used to compare BRFS time between the two treatment groups. The Kaplan-Meier method will be used to obtain the estimates of median BRFS associated with each treatment. The 95% CI of the median BRFS time will also be provided.

The syntax with SAS using the LIFETEST procedure will be:

CCI [REDACTED]

The Cox Proportional hazard model will be fitted to compute hazard ratios and the corresponding 95% CI with treatment group, country (China as reference), nested effect centre(country) (the largest centre as reference) and Gleason score on prostatectomy specimen (in categories: ≤ 6 / $= 7$ / ≥ 8 , with ≤ 6 considered as the reference) as fixed factors.

The syntax with SAS using the TPHREG procedure will be:

CCI [REDACTED]

Interactions between treatment group and each covariate (country, centre(country) and Gleason score) will be tested one by one in separate models as follows:

CCI

P-value of covariates effect as well as interactions effect will be provided. Interaction will be considered as suggestive if p-value < 0.20. Suggestive interaction will be kept:

CCI

The validity of the model will be checked as follows:

- *Check of hypothesis of proportional hazards (graphically),*

This check of hypothesis of proportional hazards can be performed using plots the log of negative log of estimated survivor functions versus the log of time.

The syntax with SAS using LIFETEST procedure will be:

CCI

If the curves are parallel then the hypothesis is checked.

Results will be presented in terms of hazard ratios associated with 95% CI and p-value for treatment group and each other fixed factors.

Survival curves for each treatment group will be plotted on the same graph. Median BRFS time for each group and number of events will be provided.

Should there be a suggestive country*treatment interaction or a centre(country)*treatment interaction, BRFS will also be analysed respectively by country/centre in order to describe any possible country/centre effect. Similarly, should there be a suggestive Gleason score*treatment interaction, BRFS will also be analysed by Gleason score categories (≤ 6 / $= 7$ / ≥ 8 , with ≤ 6 considered as the reference) in order to describe treatment effect within each subgroup.

Sensitivity analyses:

If a patient had at least two consecutive missing visits before the BR, a sensitivity analysis will be performed by censoring this patient at the date of the last visit preceding the missing consecutive visits (cf Section 3.2.10 for derived BRFS).

If patients died (whatever the cause) without BR, a sensitivity analysis will be performed by considering the death as an event (cf Section 3.2.10 for derived BRFS).

If lost to follow-up (prior to BR) is $\geq 5\%$. Baseline characteristics will be compared between groups of lost to follow-up and the other patients. If the lost to follow-up baseline characteristics differ from those of the other patients (as shown by 95 % CI), a sensitivity analysis will be performed excluding the lost-to follow-up patients.

Sensitivity analyses will be performed on ITT population on the first 61 BR events and repeated on the number of BR events observed until the end of the study if there is a difference of at least 5% of number of events (i.e. ≥ 65 events). The Log-rank test will be provided as well as the Cox Proportional hazard model. The interactions will be tested only if suggestive interactions were founded in the main analysis.

The primary efficacy analyses are summarised in the table below:

	ITT population		mITT population	PP population
	61 BR events	All BR events	All BR events	All BR events
Main analysis	X ⁽¹⁾	X	X	X
Sensitivity analysis 1 (censoring of patients with missing visits)	X	X ⁽²⁾		
Sensitivity analysis 2 (death as an event)	X	X ⁽²⁾		
Sensitivity analysis 3 (excluding lost-to-FUP patients)	X	X ⁽²⁾		

(1) Primary analysis

(2) Only if the number of BR events observed until the end of the study is different of at least 5% (i.e. ≥ 65 events)

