1.2.1.1. Inclusion criteria

Each patient must meet the following criteria:

- Provide written informed consent by the patient prior to any study-related procedure
- Men aged ≥ 18 years
- Histo-pathologically confirmed adenocarcinoma of the prostate
- Radical Prostatectomy with curative intent performed no more than 8 weeks before randomisation
- High-risk criteria of disease progression, defined as follows:
 - Gleason score ≥ 8 on prostatectomy specimen, and/or
 - Pre-RP PSA level ≥ 20 ng/mL, and/or
 - Primary tumour stage 3a (pT3a) (with any PSA and any Gleason score)
- Post-RP PSA levels ≤ 0.2 ng/mL at 6 weeks.
- Eastern cooperative oncology group (ECOG)/world health organisation (WHO) performance status of 0 to 1

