1.3.2.1. Efficacy assessments

PSA

Blood samples for PSA testing will be taken every 3 months (except at Visit 2 (Baseline, Day 1 Month 0) where PSA level is not required).

Biochemical Relapse

Biochemical Relapse definition: increased PSA >0.2 ng/mL confirmed by a second measurement performed 4 to 6 weeks later. The time-point at which the first elevated PSA measurement is >0.2 ng/mL is recorded will be deemed to be the time of BR.

To note, for the identification of BR; all PSA samples will be taken into account, even if several samples are within the same time windows.

Clinical disease progression

Clinical disease progression is defined as evidence of local/locoregional recurrence and/or lymph node involvement and/or distant metastases documented by relevant standard investigations (such as ultrasound (US) guided biopsy, X-ray, computed tomography (CT) scan, or magnetic resonance imaging (MRI) guided biopsy).

Survival status

Survival status will be recorded at each visit.

Serum Testosterone

Serum testosterone in the triptorelin treatment group will be recorded at baseline, 3, 6 and 9 months. It will be assessed both as a continuous and as a qualitative variable (< 50 ng/dL / ≥ 50 ng/dL).

Health-Related Quality of Life

Health-Related Quality of Life (HRQoL) will be assessed using the FACT-P questionnaire, version 4, and the 36-item short form (SF-36) health survey, version 2 in both treatment arms at Baseline, 9, 24, and 36 months..

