3.2.1.2.5. PSA level

The PSA level (ng/ml) at each visit (except at Visit 2 (Baseline, Day 1 Month 0) where PSA level is not required) will be described using descriptive quantitative statistics.

PSA level will be described both in its continuous format and in categories (≤ 0.2 ng/ml; >0.2 ng/ml - <4 ng/ml; ≥ 4 ng/ml - <10 ng/ml; ≥ 10 ng/ml)

The percentage change from baseline (defined as the screening values) will be also presented.

In addition, a shift table of the change in categories between baseline and each visit will be presented.

At baseline the last test available before first injection of treatment will be used. Otherwise, in case of several samples (with a result) in the same time windows (excluding the confirmation samples), the value of the last sample will be used.

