3.2.1.3. *Exploratory efficacy analysis*

To identify prognostic factors among Gleason score on prostatectomy specimen ($\leq 6 / = 7 / \geq 8$, with ≤ 6 considered as the reference), country, Pre-RP PSA level ($<20 / \geq 20$ ng/mL), primary tumour stage (T1 / T2 / T3 / T4 with T3 considered as the reference) and age (<65 years / ≥ 65 years) are associated with BRFS outcome, Cox proportional hazard regression models will be used. Each parameter will be analysed in an univariate model where the hypothesis of proportional risks will be checked graphically. Significant parameters at a 20%-level will be retained for the multivariate Cox model. Associations between significant parameters will be tested in order to keep only non correlated variables in the multivariate model. The association between two categorical or binary variables will be tested using Chi-square or Fisher's exact test. Associations will be considered as statistically significant if $p < 0.01$. A backward selection method will be used to identify the final set of prognostic factors (exit p-value set to be 0.05). Treatment will then be added to this final model to assess the effect of treatment when adjusted for these factors.

The syntax with SAS using the PHREG procedure will be:

```
CCI [REDACTED]
```

CCI [REDACTED]

3.2.2. *Safety*

Safety analysis will be analysed on safety population according to the actual treatment approach followed.

3.2.2.1. *Adverse events*

Adverse events will be graded by the investigator according to the NCI CTCAE version 4.0.

AEs will be coded according to the Medical Dictionary for Regulatory Activities (MedDRA; version 16.0) and will be classified by PT and SOC.

Listings will be presented for all patients (description, time to onset, duration, seriousness, grade, relationship to study drug, action taken and outcome) and sorted by treatment group, patient id, start time of AEs, primary system organ class, preferred term and verbatim text for all adverse events recorded during the study.

Listings of serious adverse events (SAE), adverse events leading to study withdrawal, leading to study drug discontinuation, drug related adverse events, adverse events with NCI CTC Grade > 2 and listings of deaths will also be presented.

Treatment Emergent Adverse Events (TEAE) will be flagged (*) in the adverse events listing and will be summarised.

For the triptorelin treatment group, a TEAE is defined as any AE that occurs during the active phase of the study if:

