3.2.14. Pooling of Centres

It is not planned to perform a subgroup analysis on individual or groups of centres. To compute hazard ratios on the primary endpoint a Cox Proportional hazard model will be fitted including treatment group, Gleason score, country and pooled centres. In each country, the centres with a randomized number of patients strictly above 10 will be pooled in one centre.

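### The Cox model for BRFS and the prognostic search leave out the screening post-RP PSA, the baseline of the marker whose crossing of 0.2 ng/mL defines relapse

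*SAP*

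**What the plan says.** **Entry and event.** SAP 1.2.1.1 requires "Post-RP PSA levels ≤ 0.2 ng/mL at 6 weeks". SAP 1.3.2.1 defines biochemical relapse (BR) as "increased PSA >0.2 ng/mL confirmed by a second measurement performed 4 to 6 weeks later", dated at the first raised value. The two limits meet with no gap.

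**Baseline PSA.** The schedule (1.3.3) has a PSA sample at screening and none at Visit 2. The derivation of time from surgery to screening in 3.2.10 shows that screening follows the prostatectomy. In 3.2.1.2.5 the screening sample is the PSA baseline: "The percentage change from baseline (defined as the screening values) will be also presented".

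**Primary comparison.** "A log-rank test (two-sided) will be used to compare BRFS time between the two treatment groups" (3.2.1.1). The text names no covariate or stratum for this test.

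**Cox model.** The factors in 3.2.1.1 are treatment, country, "nested effect centre(country) (the largest centre as reference) and Gleason score on prostatectomy specimen". Section 3.2.14 repeats the list: "a Cox Proportional hazard model will be fitted including treatment group, Gleason score, country and pooled centres".

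**Prognostic search.** Section 3.2.1.3 opens with "To identify prognostic factors among Gleason score on prostatectomy specimen" and goes on to country, pre-RP PSA (below 20 against 20 ng/mL or more), tumour stage and age. The only PSA among the candidates is the one taken before surgery.

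The SAS code is redacted, so these statements rest on the written factor lists.

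**The concern.** BR is a threshold crossing of the same marker that is capped at entry. A man who starts just under 0.2 ng/mL has almost no distance to cover, while a man who starts near 0.01 ng/mL needs more than four doublings. Baseline PSA is thus the starting value of the outcome variable, which sets it apart from an ordinary prognostic factor.

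Elsewhere the SAP uses such values: 3.1.5 adjusts quantitative variables for baseline when it was measured, and the HRQoL model includes baseline. That rule does not formally cover time-to-event endpoints, so there is no contradiction, but the same reasoning applies to BRFS.

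No other planned analysis fills the gap. The shift table in 3.2.1.2.5 has 0.2 ng/mL or less as its lowest category, so every eligible man starts in the same cell. The baseline characteristics in 1.3.2.3, on which 3.2.6 draws, list the last PSA before surgery and not the value after it. At stake are the precision of the reported hazard ratio, the handling of a chance imbalance in near-threshold men, and a prognostic search that never tests this variable.

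**Working it through.** **1. The plan's own figure.** Inputs from 1.3.4: BR at 36 months of 40% against 20%, two-sided 5%, power 90%, 1:1 allocation, 226 patients, 61 events.

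- HR = ln(0.8)/ln(0.6) = 0.437.
- Events (Schoenfeld) = 4 × (1.960 + 1.282)² / (ln 0.437)² = 61.3. With 61 events, power is 89.9%.

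The 61 events are reproduced. The HR of 0.437 comes from overall risks, so it is a marginal (population-average) effect, and the sizing does not depend on covariate adjustment.

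**2. Distance to the threshold.** With a constant doubling time d, the time from entry PSA p to 0.2 ng/mL is d × log2(0.2/p). The SAP gives no doubling time; d = 6 months is assumed.

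| Entry PSA (ng/mL) | Months to 0.2 |
|---|---|
| 0.19 | 0.4 |
| 0.15 | 2.5 |
| 0.10 | 6.0 |
| 0.05 | 12.0 |
| 0.01 | 25.9 |

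With d = 3 or 12 months the times halve or double; their order does not change.

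**3. Effect on power.** The SAP gives no prognostic strength for post-RP PSA, so a hazard ratio per SD is assumed for a normally distributed covariate. The overall risks are held at the plan's 40% and 20%.

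Analysis at 61 events:

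| Assumed HR per SD | Cox power, unadjusted | Cox power, adjusted | Gain (points) |
|---|---|---|---|
| 1.5 | 90% | 92% | 2 |
| 2.0 | 87% | 91% | 4 |
| 2.5 | 89% | 95% | 6 |

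The log-rank test in separate runs at 61 events gives 90%, 89%, 90% and 88% for HR 1.0, 1.5, 2.0 and 2.5 per SD. Differences of a point or two between such runs are simulation noise.

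A second set has 2000 runs per setting and follow-up cut at 40 months, which gives about 68 events:

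| Assumed HR per SD | Unadjusted | Adjusted | Mean HR, unadjusted | Mean HR, adjusted |
|---|---|---|---|---|
| 1.0 | 91% | 91% | 0.43 | 0.43 |
| 1.5 | 91% | 93% | 0.43 | 0.42 |
| 2.0 | 90% | 95% | 0.43 | 0.40 |
| 3.0 | 91% | 98% | 0.43 | 0.35 |

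Type I error lies between 4.3% and 5.2% in every setting, with or without the covariate.

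**4. Chance imbalance.** With 113 per arm, the standard error of the between-arm difference in mean PSA is √(2/113) = 0.133 SD. A difference at 1.96 standard errors is 0.26 SD. It would multiply an unadjusted HR by about exp(0.26 × ln h), where h is the HR per SD: 1.11, 1.20 and 1.27 for h = 1.5, 2.0 and 2.5. This is approximate and describes an unlucky allocation, not the expected one.

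**The case against.** A reader might infer that the omission biases the treatment effect towards 1 and costs the trial its power. Simulations that take 0.437 as the HR conditional on PSA do show unadjusted Cox power of 88%, 83% and 80% at HR 1.5, 2.0 and 2.5 per SD. The documents do not support that reading. The plan derives 0.437 from overall risks of 40% and 20%, so using it as a conditional effect builds a weaker marginal effect into the simulated trial. With the overall risks held at the plan's values, the unadjusted HR stays at 0.43 and the adjusted HR moves away from 1. That is non-collapsibility: the two hazard ratios are different estimands, and under randomisation the unadjusted one is not biased.

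Other objections stand in part:

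- The primary test is the log-rank test, so adjusting the Cox model changes nothing in the primary inference. This is correct, and it limits the point to the hazard ratio and the exploratory search.
- The SAP gives no distribution of post-RP PSA, assay limit or prognostic strength. If most values are undetectable, the covariate carries little information. To call it a major driver of BR would go beyond the documents.
- BR needs confirmation 4 to 6 weeks later, which filters transient rises, so a start near 0.2 ng/mL does not guarantee an early event. Nor is it shown that such early events say little about treatment.
- Screening PSA is summarised as a continuous variable, so an imbalance could be seen. It would still not be corrected.
- Covariate choice is discretionary, and omitting one is not an error. That is fair, but this covariate is the baseline of the outcome marker and is already collected.

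**Conclusion.** The point holds as a near-costless improvement to the Cox and prognostic analyses. It is not a flaw in the primary test. The shared 0.2 ng/mL limit and the absence of screening PSA from both written lists are plain in the text. The log-rank comparison remains valid at about its planned 90% power.

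The expected loss is about 2 to 6 power points in the Cox treatment comparison. This rests on an assumed hazard ratio of 1.5 to 2.5 per SD of baseline PSA, a normally distributed covariate and overall risks as planned. The loss falls towards zero if PSA is weakly prognostic or mostly undetectable. Correction of an unlucky imbalance near the threshold and a prognostic search that includes the marker's own starting value are lost as well.

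**What to change.** - In 3.2.1.1, with 3.2.14 brought into line, pre-specify log2 of the screening PSA as a continuous covariate in the BRFS Cox model. The minimum is a pre-specified supportive Cox model that contains it.
- Add the same variable to the candidates in 3.2.1.3.
- Define it as the last value before randomisation. The baseline rule in 3.2.1.2.5 refers to the first injection, which surveillance patients do not receive.
- Set values below detection to the limit, and extend the 3.2.13 rule, now written for summaries, to model covariates.
- Keep the log-rank test as the primary test.
- State that the adjusted hazard ratio is conditional and may lie further from 1 than the unadjusted one.

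The cost is SAP wording and one more parameter in the Cox model. No new data are needed.

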RAP Final Version 3 [22-JUL-2019]

15/248

CCI

1 Adverse events (AEs) will only be collected until Visit 5/Month 9; this corresponds to three months after the last triptorelin injection for those patients in the triptorelin group. After this visit, only AEs and SAEs related to triptorelin according to Investigator's judgement should be reported (with the exception of AEs resulting in death that should be reported until the end of the study).

Patients will not be withdrawn from the study if study medication is discontinued. Follow-up will continue for all patients every 3 months and for at least 36 months.

1.3.4. *Planned sample size*

It is planned to recruit 226 patients in approximately 10 centres in two countries (China and Russia) according to the Sample Size Determination.

The sample size estimation was based on the primary efficacy endpoint of BRFS. Assuming that with RP alone, the probability of biochemical (PSA) relapse as defined in Section 4.2.1 of the study protocol at 36 months after RP is 40% in high-risk patients (Section 2.1 of the study protocol, Table 1), and anticipating that immediate adjuvant hormonal therapy added to RP will reduce this probability to 20% (percentage considered to be clinically relevant), 113 patients per treatment group (226 in total) are required in order to detect such a difference using a two-sided log-rank test at a significance level of 5% and a power of 90%, assuming a common 1% exponential dropout rate (corresponding to an approximate 5% dropout rate per year).

These 226 patients are required to observe 61 BR in order to achieve 90% power. For patients with no sign of disease progression at 36 months post-randomisation, monitoring will continue until the 61 BR events are observed at the study global level. If the 61 events are observed before all patients complete the 36 months post-randomisation monitoring period, the study will be continued until those patients reach their 36 month visit (Visit 14).

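### A p<0.20 rule for keeping treatment interactions can change the BRFS Cox model, and the readable text does not say which treatment hazard ratio is then reported

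*SAP*

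**What the plan says.** SAP 3.2.1.1 compares BRFS between arms with a two-sided log-rank test. It then fits a Cox model for the HR and its 95% CI, with treatment, country, centre nested in country, and Gleason category as fixed factors. Section 3.2.14 lists the same terms: "a Cox Proportional hazard model will be fitted including treatment group, Gleason score, country and pooled centres".

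Section 3.2.1.1 goes on: "Interactions between treatment group and each covariate (country, centre(country) and Gleason score) will be tested one by one in separate models". The decision rule is "Interaction will be considered as suggestive if p-value < 0.20. Suggestive interaction will be kept", followed by blacked-out code. On reporting it says: "Results will be presented in terms of hazard ratios associated with 95% CI and p-value for treatment group and each other fixed factors".

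If the country or centre interaction is suggestive, "BRFS will also be analysed respectively by country/centre in order to describe any possible country/centre effect", and there is a similar provision for Gleason categories. For the sensitivity analyses, "The interactions will be tested only if suggestive interactions were founded in the main analysis". Section 3.2.14, however, opens with: "It is not planned to perform a subgroup analysis on individual or groups of centres".

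**The concern.** Once a treatment interaction is in a Cox model, there is no longer one treatment HR. There is an HR at each level of the interacting factor, and any single figure is either the HR at a reference level or an average under some weighting. The readable text promises an HR, CI and p-value for treatment without saying which of these is meant when the rule has kept an interaction.

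The screen is loose (p<0.20) and is applied three times, so it will often fire when nothing is there. The HR printed beside the log-rank result could then come from a model chosen by chance. The main analysis is also repeated at the end of the study and in the mITT and PP populations, and the sensitivity analyses take their cue from the main one. Unless the reported model is fixed, HRs meant to be compared may not come from the same model.

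The second issue is separate: one section plans a by-centre analysis under a condition, and another says no centre subgroup analysis is planned.

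**Working it through.** **The plan's own figure first.** The sample size (SAP 1.3.4) was derived "using a two-sided log-rank test at a significance level of 5% and a power of 90" per cent, with relapse probabilities at 36 months of 40% and 20%.
- HR = ln(0.8)/ln(0.6) = 0.437.
- Events by Schoenfeld's formula = 4 × (1.960 + 1.282)² / (ln 0.437)² = 61.27. The plan's 61 is reproduced.
- Power with 61 events = 0.899.

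No interaction term enters this calculation or the log-rank test, so the screen leaves both untouched.

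**Chance that the rule fires with no true interaction.** Inputs from 3.2.1.1: threshold 0.20 and up to three tests. For k independent tests, P(at least one kept) = 1 − 0.8^k.
- k = 2: 1 − 0.64 = 0.360.
- k = 3: 1 − 0.512 = 0.488.
- Three tests with unknown dependence: between 0.20 (complete overlap) and 0.60 (sum of the three levels).

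**Which k applies depends on the centre structure.** Section 3.2.14, as worded, pools the centres in each country that have more than 10 randomised patients. The plan expects about 10 centres for 226 patients, an average of 226/10 = 22.6. If every centre exceeds 10, each country has one pooled centre. Centre within country then adds nothing to country, and two tests remain. If a country keeps two or more centre levels, there are three.

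**Simulation check.** All runs use 226 patients at 1:1, HR 0.437, dropout of 5% per year and no true interaction. Country shares, Gleason mix and centre counts are assumptions, because the plan gives no mix.

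| Centre levels per country | Test | P(at least one p<0.20) |
|---|---|---|
| 1 (two tests) | likelihood ratio | 37–39% |
| 1 (two tests) | Wald | 34–35% |
| 2 (three tests) | likelihood ratio | 46–51% |
| 5 (three tests) | likelihood ratio | 59–63% |

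The last row can pass the 60% bound because, with many small centres, the centre interaction test rejected in 34–37% of runs instead of 20%. The simple formulas are therefore fair for few centre levels and low for many.

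**The two sections side by side.**
- Base model: 3.2.1.1 and 3.2.14 agree on treatment, country, centre and Gleason. Only the keeping rule departs from it.
- Centre analysis: 3.2.1.1 provides for one if the centre interaction is suggestive; 3.2.14 says none is planned and makes no exception. These conflict as written. The conflict has practical effect only if some country keeps at least two centre levels, which is not the 36% case.

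**The case against.** The strongest objection is that the rule ends in a colon and the code after it is blacked out. That code may show exactly which HR is reported, and text lost to redaction is not a defect of the plan. This stands, and it rules out any claim that the definition is missing from the full plan.

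Second, the readable text leans towards the main-effects HR. Interactions are tested in separate models, results are promised for treatment and the other fixed factors, and the stratum analyses are additional and descriptive. This is fair. It makes the intended answer likely, but it does not cancel a rule that a suggestive interaction is kept.

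Third, the covariates, threshold and testing order are all set in advance, and the confirmatory comparison is the log-rank test. Both are true, and they limit the weight of the point.

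A reader might also infer that 3.2.14 independently contradicts 3.2.1.1 by prescribing a model with main effects only. It does not: both sections list the same base terms, and 3.2.14 is about pooling and does not exclude further terms. Nor do the documents support the inference that the reported HR would become much less precise, for instance by being read at the China or Gleason ≤6 reference level. That would require knowing the hidden code as well as the country and Gleason mix.

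**Conclusion.** The point holds as a minor one. A rule driven by the data can alter the BRFS Cox model. With no true interaction it would do so in about 36% of trials with two independent tests and 49% with three. Those figures assume independent tests holding their nominal level, and which applies depends on the centres left after pooling. The readable text does not name the treatment HR that is then reported, and no specific change in the HR or its standard error is claimed.

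The mismatch over by-centre analysis between 3.2.1.1 and 3.2.14 is separate and can be seen directly in the text.

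Only the supportive Cox HR, CI and p-value for BRFS are concerned. A reader might take this as a threat to the type I error or power of the primary test; it is not one. The log-rank test, the Kaplan-Meier results and the 61 events do not depend on the screen. Section 3.2.1.2 excludes interaction tests for EFS, OS, disease-specific mortality and PSA doubling time.

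**What to change.** In 3.2.1.1, state in prose: *The reported BRFS treatment HR, 95% CI and p-value come from the main-effects Cox model (treatment, country, pooled centre, Gleason) whatever the interaction results, in the main and sensitivity analyses. Models with a kept interaction, and analyses by country, centre or Gleason category, are supportive.* Check that the code agrees.

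In 3.2.14, add to the sentence on centre subgroups an exception for the descriptive by-centre analysis in 3.2.1.1.

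The interaction tests and stratum analyses stay. The cost is two sentences, one clause and a check of the code; the main-effects model and the stratum outputs are already planned. The downside is that, if a real interaction exists, the headline HR is an average over differing effects. The planned stratum analyses would then describe the differences.
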